9.4 Secondary Effectiveness Endpoint Analysis

The study secondary endpoint is defined as within subject comparison of ADLs and UPDRS across Visit 1-3 captured as defined in the protocol. Statistical analyses will be performed incorporating intra-subject correlation for repeated measures, and as for the primary endpoint the statistical objective is to demonstrate that Parkinson's disease action tremor is reduced under treatment with the Cala Trio device.

Null and alternative hypotheses are analogous to those shown above.

9.5 Additional Exploratory Effectiveness Analyses

Additional exploratory analyses include:

- Patient Session Impression of Improvement (PSI-I)
- UPDRS modified Part III (tremor tasks only) – subset relevant to non-stimulated hand
- UPDRS modified Part III (tremor tasks only) and ADL pre- versus post-stimulation within each visit
- ADLs based on recall
- Product Survey
- Device usage metrics
- CGI-S/I, PGI-S/I

Note that the same UPDRS modified Part III (tremor tasks only) are collected on the non-stimulated hand in order to determine if the device has a bilateral effect.

The listed analyses will be evaluated using analogous statistical methods as described for the primary and secondary endpoints.

9.6 Planned Analyses

All participants in this study will be using the same device as the commercial users of Cala Trio diagnosed with ET, with a common user interface workflow. As with all commercial users, an accelerometer on the device will measure tremor power before and after a subset of 40-minute therapy sessions (every session for the first 40 sessions, followed by every 7th session thereafter). Subject-reported ratings of the therapy sessions (improved, no change, worsened) will be recorded after the acceleration measurements on the device.

A study of safety and efficacy of Transcutaneous Afferent Patterned Stimulation (TAPS) for reduction of action tremor in Parkinson's Disease (PD)	Protocol PD-02
	Rev A; 1-OCT-2020

The analysis will evaluate de-identified data from up to 50 subjects who complete Cala Trio therapy sessions during 4 weeks of at-home use. Subjects will be given instruction on how to calibrate the device's stimulation to their hand tremor frequency and will be instructed to use the therapy twice daily at home. Therapy efficacy will be quantified using improvement in tremor power pre- and post- stimulation. Tremor severity will be visually rated for all subjects by an expert rater according to UPDRS and the ADL score will be noted.

Formal analyses of the primary and secondary endpoints will be conducted after completion of study. It will take place once 50 subjects have reached the 4-week visit, at which time analyses subgroups of interest will also be investigated, tabulated and reported.

Study hypotheses will be tested for p-values of 0.05 and 0.01.

9.7 Sample Size and Power

The study sample size (N) is predicated on primary endpoints as detailed above. Assuming same effect from the ET-14 data, at $p = 0.01$ we have the following results.

Metric	p value	N
Kinematic measurements for study duration of 2 weeks	0.01	40
Kinematic measurements for study duration of 4 weeks	0.01	30

Under these effect sizes, assuming up to 10% data attrition and with a paired difference test at 0.01 alpha against the null hypothesis of no change from baseline, the 34 to 50 subject analysis provides at least 90% power for simultaneous testing of the primary endpoint.

10.0 Study Administration

10.1 Institutional Review Board Approval

The study protocol will be reviewed and approved by the Investigator's IRB prior to subject enrollment. The Sponsor and the IRB prior to implementation must approve proposed significant changes to the clinical study protocol. A significant change is one which may increase the risk or present a new risk to a subject, affects the subject's rights or welfare, or which may adversely affect the scientific validity of the study.

Investigators are responsible for obtaining and maintaining annual renewal of the study by their IRB (or according to renewal schedule imposed by the IRB).

10.2 Amending the Protocol

The protocol, subject informed consent, or other clinical investigation documents shall be amended as needed throughout the clinical investigation. Proposed amendments to the protocol shall be agreed upon between the Sponsor and Investigator (or delegate). The amendments to the protocol and the subject's informed consent form shall be notified to, or

A study of safety and efficacy of Transcutaneous Afferent Patterned Stimulation (TAPS) for reduction of action tremor in Parkinson's Disease (PD)	Protocol PD-02
	Rev A; 1-OCT-2020

approved by, the IRB and regulatory authorities. The version number and date of amendments shall be documented.

10.3 Privacy and Confidentiality

Subject data obtained in connection with this clinical study will be treated as confidential and will be disclosed only as required by law. A number will identify subjects, not a name. The subject informed consent discloses how subject information is collected and used, and all subjects must consent in writing prior to any study-related treatments.

10.4 Record Retention

Investigators will maintain complete, accurate and current study records in accordance to the requirements in the IDE regulation (21 CFR 812).

These records shall be maintained for a period of two years after the latter of the following two dates: the date on which the investigation is terminated or completed, or the date that the records are no longer required for purposes of supporting a regulatory submission.

10.5 Device Accountability

Device accountability records will be maintained at the study site. Devices used during the study will be recorded in the device accountability and disposition logs.

10.6 Sponsor Responsibilities

The Sponsor (Cala Health, Inc.) is responsible for:

- Ensuring that the study is designed and managed in compliance with all appropriate regulatory standards and is conducted according to the protocol
- Selecting qualified investigators and providing them with the information and materials necessary to conduct this study in compliance with the protocol and local applicable regulatory requirements
- Providing appropriate training to Investigators, site staff and all sponsor representatives to conduct this study in compliance with the protocol and local applicable regulatory requirements
- Securing compliance with the clinical protocol, investigator agreement, and local regulations
- Confirming that IRB review and approval are obtained prior to subject enrollment or conducting protocol-required testing
- Ensuring that the Investigators and the reviewing IRB are promptly notified of significant new information about this clinical study
- Supervising the overall conduct of the study: ensuring proper monitoring of the clinical study and data, analyzing data (including evaluations of AEs) and preparing study reports
- Controlling the distribution of the device(s) under investigation.

10.7 Investigator Responsibilities

The Investigator is responsible for the following:

A study of safety and efficacy of Transcutaneous Afferent Patterned Stimulation (TAPS) for reduction of action tremor in Parkinson's Disease (PD)	Protocol PD-02
	Rev A; 1-OCT-2020

- Ensuring sufficient time and resources (including qualified staff and facilities) are available to manage the day-to-day conduct of the study, and ensuring data integrity and the rights, safety and well-being of subjects
- Obtaining approval from the IRB, including subsequent protocol amendments and changes to the subject informed consent and obtaining renewals throughout the duration of the study
- Compliance with the clinical study protocol and applicable regulatory requirements
- Investigational device accountability and use of the investigational device in accordance with the approved protocol
- Reporting all SAEs to the Sponsor as soon as possible after knowledge of the event, and to the IRB as specified in the requirements.

11.0 Publication

The Sponsor may disclose the results of the study through a publication or any other public disclosure. A Publications Review Committee may be formulated to oversee the publication process. Authorship on a primary publication of the results from this study will be based on contributions to study design, enrollment, data analysis, and interpretation of results.

A study of safety and efficacy of Transcutaneous Afferent Patterned Stimulation (TAPS) for reduction of action tremor in Parkinson's Disease (PD)	Protocol PD-02
	Rev A; 1-OCT-2020

13.0 Revision History

Protocol Version	Summary of Changes	Author
A	Initial Release	[name]

2 STUDY OVERVIEW

2.1 Design and Objective

This is a prospective, single-site, single-arm, non-significant risk study designed to evaluate the Cala Trio device for action tremor in PD. Subjects will be screened for eligibility and fitted with a Cala Trio device. Subjects will wear the device at home for a period of 4 weeks, during which they will be asked to stimulate their dominant hand twice daily. The stimulation amplitude will be based on each subject's stimulation threshold. Subjects will have in-clinic assessments at enrollment, as well as before and after treatment of 4 weeks. The study timeline, reproduced from the study protocol, is illustrated below. More detail on study data follows below.

All subjects will be informed of their right to withdraw from the clinical study at any time without penalty or loss of benefits. The Investigator may prematurely discontinue any subject from the study if the Investigator feels that the subject can no longer fully comply with the requirements of the study or if any of the study procedures are deemed potentially harmful to the subject.

The study objective is to evaluate symptomatic hand tremor relief in the treated hand following stimulation with the Cala Trio device in adults with action tremor in PD over a duration of 4 weeks.

a. Visit 1

Subjects will be reminded to be in the *off* state, i.e., to skip their last dose of PD medication, prior to their telemedicine Visit 1. The following assessments will occur:

- Screening activities including medication review and medical history. No medical records will be used for this study, so all eligibility criteria will be based upon self-reported information from each subject and verification by qualified study staff.
- Tremor assessments (while in the *off* state) including:
 - Modified MDS Unified Parkinson's Disease Rating Scale Part III (MDS-UPDRS) to confirm eligibility will be rated by the PI
 - Bain & Findley Activities of Daily Living (BF-ADL) upper limb subset score will be rated by the subject based on their recall of the previous week (no props will be used)
- Demographic information, Parkinson's clinical characteristics, and wrist size and handedness will be collected based on self-reported information from subjects.

Once a subject has been confirmed to be eligible for the study, a device kit containing a stimulator, base station and band will be shipped directly to the subject's home ahead of Visit 2.

b. Visit 2

Visit 2a

Once a subject has received the device kit, device training will occur via telemedicine, as follows:

Positioning and Fastening Cala Trio

Prior to device positioning, subjects should dampen the wrist of the prescribed hand to ensure good connection between the electrodes and wrist. Subjects should position the device on the prescribed hand such that the electrodes are positioned over the median and radial nerves, and securely tighten the band.

Device Calibration

To calibrate the Cala Trio device, subjects will perform a series of postural hold tremor tasks, in which the device measures the subject's tremor frequency and sets the stimulation burst frequency based on the measured tremor frequency.

For the purposes of this study, only the outstretched postural hold tremor task will be used.

Setting Stimulation Intensity

The subject will set the stimulation intensity to an amount they can comfortably tolerate while doing light activities. Paresthesia should be perceived in the parts of the hand and/or fingers innervated by the median and radial nerves. The stimulation intensity selected during the initial amplitude calibration is saved on the device for subsequent sessions. The subject can decrease or turn off the stimulation at any point in time and may adjust their stimulation intensity from session to session to maintain the minimum paresthesia threshold.

Device Training

During the course of the visit, study personnel will instruct the subject on proper use of the device. Subjects must demonstrate competence to operate the device and comprehension of the instructions for use prior to completing the training.

Visit 2b

Once a subject is trained on the device, the subject will receive a single 40-minute therapy session with their Cala Trio. The subject will be asked to not stimulate at least 8 hours prior to this visit. The following assessments will be made prior to the therapy session and again immediately post the therapy session:

- Tremor assessments (while in the *off* state) including:
 - Modified MDS Unified Parkinson's Disease Rating Scale Part III (MDS-UPDRS) will be rated by the PI
 - Bain & Findley Activities of Daily Living (BF-ADL) upper limb subset score will be rated by the subject. The BF-ADL assessment will be performed using the subject's own household props

- CGI-S, I/PGI-S, I
 - Clinical/Patient Global Impression of Severity (CGI-S/PGI-S): The investigator or designee (CGI) and Patient (PGI) will rate the overall tremor severity prior to stimulation
 - Clinical/Patient Global Impression of Improvement (CGI-I/PGI-I): The investigator or designee (CGI) and Patient (PGI) will rate the overall tremor improvement following stimulation

Additionally, the Cala Trio will direct the subject to perform the outstretched postural hold tremor tasks before and after the stimulation session to measure tremor power. Finally, subjects will input their Patient Session Impression of Improvement (PSI-I) rating on the device after the stimulation session

Visits 2a and 2b may be combined into a single Visit 2.

c. Home-Usage

The home use portion of the study will last 4 weeks. It will include:

- 2 stimulation sessions/day preferably at the same time every day recommended as one in the morning and one in the evening.
- Motion data from the device before and after each stimulation session. Cala Trio will direct the subject to perform postural hold tremor tasks before and after the stimulation session to measure tremor power. Additionally, subjects will input their Patient Session Impression of Improvement (PSI-I) rating on the device after the stimulation session
- Weekly Bain & Findley Activities of Daily Living (BF-ADL) upper limb subset score will be rated by the subject based on their recall of the previous week (no props will be used)
- Device factory reset of the Cala Trio will occur on Day 14 of treatment via a call with study staff

d. Visit 3/Study exit

Subjects will be reminded to be in the *off* state, i.e., to skip their last dose of PD medication, prior to their telemedicine Visit 3/Study exit. The subject will be asked to not stimulate at least 8 hours prior to this visit. The subject will receive a single 40-minute therapy session with their Cala Trio. The following assessments will be made prior to the therapy session and again immediately post the therapy session:

- Tremor assessments (while in the *off* state) including:
 - Modified MDS Unified Parkinson's Disease Rating Scale Part III (MDS-UPDRS) be rated by the PI

- Bain & Findley Activities of Daily Living (BF-ADL) upper limb subset score will be rated by the subject. The BF-ADL assessment will be performed using the subject's own household props
- CGI-S, I/PGI-S, I
 - Clinical/Patient Global Impression of Severity (CGI-S/PGI-S): The investigator or designee (CGI) and Patient (PGI) will rate the overall tremor severity prior to stimulation
 - Clinical/Patient Global Impression of Improvement (CGI-I/PGI-I): The investigator or designee (CGI) and Patient (PGI) will rate the overall tremor improvement following stimulation
- Product/preference survey
- Subjects will return all study materials with provided shipping packages

A factory device reset, and re-calibration may be required if the device does not prompt a tremor task measurement of postural hold prior to starting the stimulation session.

2.2 Analysis Set

Available data on all enrolled subjects will be summarized and reported, referred to in ICH E9 (“Statistical Principles for Clinical Trials”) as the *full analysis set*.

2.3 Randomization

The study is non-randomized.

3 STATISTICAL METHODS

3.1 General Principles

- All hypothesis testing will be performed using a two-sided test at a 0.05 level of significance or a one-sided test at a 0.025 level of significance. Significance levels will be adjusted for multiple hypothesis testing where appropriate. P-values will be reported as raw uncorrected p-values and rounded to three decimal places. If a p-value is less than 0.001 it will be reported as “< 0.001.”
- Summary statistics will be reported for all analyzed variables.
 - Continuous data will be summarized using descriptive statistics appropriate for the underlying data distribution, e.g., mean, standard deviation, median, and interquartile range (first and third quartiles).
 - Categorical, non-ordered variables will be summarized using frequency counts and percentages.
 - Ordinal variables, including those specific to study outcomes – e.g., the modified Movement Disorder Society Unified Parkinson’s Disease Rating Scale (MDS-UPDRS) Part III and the Bain & Findley Activities of Daily Living (BF-ADL) scale – will be summarized using measures of central tendency and variance as opposed to frequency counts and percentages; that is, these variables will be reported using the same metrics as defined above for continuous variables.
- For events which can occur more than once in a single subject (e.g., adverse events), the percentage will be based on number of subjects experiencing the event, and both subject and event counts will be reported.
- Baseline is defined as the last measurement for the outcome of interest obtained before the exposure to study treatment.
- For time-to-event analyses, complete dates for events of interest (e.g., index treatment, outcome events, censoring), will always be used. Incomplete dates will be incorporated by defining the event as occurring on the earliest date possible given the incomplete information. E.g., a date of UNK-FEB-2018 will be incorporated into the analysis as 01-FEB-2018.
- Statistical analyses will be performed in SAS (SAS Institute, Cary, N.C.) version 9.3 or later, R (R Foundation for Statistical Computing, Vienna, Austria) version 3.2 or later,

Matlab (The MathWorks, Inc., Natick, MA) version R2016B or later, Python (Anaconda, Inc., Austin, TX) version 3.6.6 or later, or in another validated statistical software package.

3.2 Analysis Populations

As stated in section 2.2, available data on all enrolled subjects will be summarized and reported, referred to in ICH E9 (“Statistical Principles for Clinical Trials”) as the *full analysis set*.

Two analysis populations will be defined, one consisting of all available data evaluated under intent-to-treat (ITT) principles, and the other consisting of all available data evaluated under per-protocol (PP) principles. Both populations are defined in further detail below. For each analysis population, “available data” means that missing data will not be replaced or imputed, and that endpoints defined as change scores will require both baseline and follow-up data to be present to be included in analyses.

The ITT population consists of all enrolled subjects.

The PP population is defined as ITT subjects who furthermore:

- Met all inclusion/exclusion criteria (in particular, subjects enrolled but determined post-enrollment not to have met one or more eligibility criteria will be excluded from the PP population).
- Were dispensed a stimulator at the primary timepoint (visit 2b) that had been appropriately calibrated to the subject’s tremor; subjects who were dispensed stimulators at the time of visit 2b that had not been calibrated to that subject’s tremor will be excluded from the PP population.
- Remained on a stable dosage of tremor and antidepressant medications, if applicable, during the duration of the study.
- Were rated by a certified UPDRS rater at the primary timepoints (Visit 1, Visit 2b and Visit 3).

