3.0 Study Design

3.1 Overview

This is a single arm study done involving telemedicine visits and a home use period. Subjects will be seen for up to 4 telemedicine visits and will have a 4 week treatment period at home. During the treatment period, subjects will be asked to stimulate their dominant hand at home 2 times per day, preferably at the same time every day, measuring kinematics before and after every therapy session.

This study will include both subjects on levodopa and subjects taking other Parkinson's medications/unmedicated for Parkinson's.

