3.3 Inclusion Criteria

Prospective subjects must meet all of the following criteria to be eligible for study participation:

- Must be ≥ 22 years of age
- Competent and willing to provide written, informed consent to participate in the study
- Clinically significant postural tremor as defined by:
 - Dominant hand/arm exhibiting postural tremor ≥ 2 (while in the off state) as assessed by the MDS-UPDRS postural tremor score
- Stable dose of Parkinson's disease medications, if applicable, for 30 days prior to study entry
- Willing to comply with study protocol requirements including:
 - remaining on a stable dosage of Parkinson's medications, if applicable, during the duration of the study
 - no significant caffeine consumption within 8 hours of study visits
 - Having the ability to do telemedicine or video calls for study visits

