4.0 Schedule of Assessments

The following table outlines the schedule of assessment for subjects throughout the entire duration of the study.

Table 1. Schedule of Assessments

	Assessment	Visit 1 (screening/ enrollment)	Visit 2a/b (device calibration/ training)	Home Use	Visit 3 (Study Exit)	After device is returned to Cala
	Time	Day -7	Day -1/0 (+ 7 days)	Days 1-28	Day 28 (+ 7 days)	N/A
PI or designee	Informed Consent	X				
	Medical History & Demographics	X				
	Medication Review	X				
	UPDRS modified Part III	X				
	Confirmation of Subject Eligibility	X				

A study of safety and efficacy of Transcutaneous Afferent Patterned Stimulation (TAPS) for reduction of action tremor in Parkinson's Disease (PD)	Protocol PD-02
	Rev A; 1-OCT-2020

	UPDRS modified Part III (pre/post stim)		X		X	
	CGI-S/I		X		X	
Cala	Device Calibration & Training		X			
	Final device upload and device unassignment followed by factory reset			Factory reset on Day 14		X
Subject	Stimulation & PSI-I		X	2x per day	X	
	Kinematics		Pre/Post stim	Pre/Post stim	Pre/Post stim	
ALL	B&F ADLs (recall)	X		1x per week	X	
	B&F ADLs (pre/post stim)		X		X	
	PGI-S/I		X		X	
	Product Survey				X	
ALL	Adverse Events	X	X	X	X	

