3.10 Subgroup and Covariate Analysis

Primary and secondary endpoints will be investigated for each of the following subgroups:

- Gender (M/F)
- Age (< 65 vs. \geq 65 years)
- Age onset of hand tremor in PD (by median split)
- Duration of PD from beginning of tremor symptom (by median split)
- Tremor Medications (On/Off)
- Antidepressant medications (On/Off)
- Preset Stimulation amplitude (by median split)
- Average Final Stimulation amplitude (by median/mean split)
- Stimulation calibration frequency (by median split)
- Baseline tremor severity as measured by UPDRS (by median split)
- Baseline tremor severity as measured by BF-ADL scale (by median split)
- Pre-stimulation tremor power, aggregated over first week (by median split)

Comparisons within subgroups will be performed using the same statistical tests as specified above for the overall cohort.

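### The SAP's per-protocol medication rule names tremor and antidepressant drugs instead of the Parkinson's medication that the protocol restricts, and no scheduled data after Visit 1 support it

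*SAP*

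**What the plan says.** **Protocol.** Section 3.3 sets two medication conditions, both about Parkinson's drugs. The entry condition is "Stable dose of Parkinson's disease medications, if applicable, for 30 days prior to study entry". The in-study condition is part of the subject's willingness to comply: "remaining on a stable dosage of Parkinson's medications, if applicable, during the duration of the study". Section 3.1 describes the population by the same drug class: "This study will include both subjects on levodopa and subjects taking other Parkinson's medications/unmedicated for Parkinson's". Neither antidepressants nor a class of tremor medications appears anywhere in the protocol. In the Section 4.0 schedule, the row "Medication Review" is marked at Visit 1 and is blank for Visit 2a/b, home use and Visit 3.

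**SAP.** Among the conditions for the PP population, Section 3.2 requires that the subject "Remained on a stable dosage of tremor and antidepressant medications, if applicable, during the duration of the study". Section 3.10 uses the same two classes as subgroups: on or off tremor medications, and on or off antidepressants. The SAP defines neither class. Section 3.6 says that the primary and secondary endpoints will be tested on both the ITT and PP populations, while Section 3.12 makes the full analysis set the primary cohort.

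**The concern.** A PP set is meant to hold the subjects who followed the protocol. Here the stability clause is nearly the protocol's own sentence with the drug class exchanged. It therefore tests something the protocol does not require and does not name what the protocol does require.

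This matters because the study has a single arm and no blinding. If a subject's Parkinson's medication changes during the four weeks, the change is a rival explanation for any difference between Visit 2b and Visit 3, and there is no control arm to absorb it. The PP set is the only planned population that could take such subjects out.

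**Working it through.** The plan gives no figure on this point, so the check is a comparison of the texts.

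**Step 1. Apply both rules to the same subject.**

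| Change during the study | Protocol 3.3 | SAP 3.2 PP bullet |
|---|---|---|
| None | Compliant | Kept |
| Antidepressant only | Compliant | Excluded |
| Parkinson's drug only | Not compliant | Excluded only if the drug is counted as a tremor medication, which is undefined |
| Both | Not compliant | Excluded, through the antidepressant clause |

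The two rules disagree in the second row. In the third, the SAP's answer depends on a classification that it does not supply.

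**Step 2. See whether another PP condition closes the gap.** SAP 3.2 also requires that all eligibility criteria were met. That brings in the 30-day entry rule and the stated willingness to stay stable. Both are judged at entry, so a subject can satisfy them and still change a Parkinson's dose in week 2.

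**Step 3. Look for the data.**
- Protocol 3.13 names only Parkinson's medications and their schedule for documentation at screening. The Visit 1 medication review is not described further.
- The procedures for Visit 2b, home use and Visit 3 (Protocol 3.16.2 to 3.18) list no medication review, in agreement with the schedule.
- Protocol 8.1 has deviations recorded on case report forms when they come to light in monitoring or otherwise. A Parkinson's dose change could be recorded that way. An antidepressant change breaches no protocol rule, so it would not be.

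The clause with no basis in the protocol is therefore also the one with no data route after Visit 1.

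**Step 4. Find which endpoints are exposed.**
- Primary (SAP 3.3): each subject's median, over sessions, of pre-stimulation divided by post-stimulation tremor power. A lasting medication change sits on both sides of every later ratio.
- Secondary 1a to 1d (SAP 3.4): before against after stimulation within one visit, so the same reasoning applies.
- Secondary 2a, 2b, 3a and 3b (SAP 3.4): Visit 2b against Visit 3. A change between those visits enters the contrast directly.

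**Step 5. Size.** The documents give no rate of medication change for either class, so the number misclassified cannot be computed. What can be stated is the weight of one subject. The SAP considers 34 to 50 subjects for analysis, and the protocol synopsis allows up to 60. One subject is then 1/34 = 2.9%, 1/50 = 2.0% or 1/60 = 1.7%. No PP set size is given, so this is a scale and not an estimate of the effect.

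**The case against.** The best defence is that in a SAP about action tremor in Parkinson's disease, tremor medications can naturally be read as the subjects' Parkinson's drugs. On that reading the third row of the table resolves correctly, and the antidepressant clause is an extra restriction that a PP definition is free to add. Part of this stands. A reader might infer that the SAP applies a plainly wrong rule and would keep subjects who changed a Parkinson's drug. The documents do not support that, because the term is undefined. What they show is a mismatched and undefined class. The defence does not cover the antidepressant clause, which has neither a stated reason nor a data source.

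A reader might also infer that nobody's stability can be determined. That goes too far. Deviation reporting exists, and staff speak to subjects on Day 14 and at Visit 3. The case report forms are not among the documents, so what they record is unknown. The supportable statement is that no collection is scheduled after Visit 1.

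A third objection is that PP results do not decide the study. That stands: SAP 3.3 tests the primary endpoint on all enrolled subjects with outcome data, and study success is not tied to the PP set. Endpoints 2a to 3b also come last in the testing sequence. Both visits are rated in the off state, which may soften the effect of a dose change, though the documents give nothing to say by how much. One caution runs the other way. Protocol 9.3 words the primary comparison as baseline to 4 weeks, and under that wording the exposure would be wider. The PP set, however, exists only in the SAP, alongside the SAP's within-session endpoint.

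Finally, a reader might take the missing levodopa subgroup as an error. The protocol describes who is enrolled but promises no such subgroup, so its absence contradicts nothing.

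**Conclusion.** The concern holds in a limited form. The PP medication criterion does not match the protocol's in-study rule, relies on an undefined class, adds an unexplained antidepressant condition, and has no scheduled data source. Misclassification is possible in both directions: certain in principle for antidepressant changes, and dependent on interpretation for Parkinson's drugs.

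The reach is the PP analyses, mainly secondary endpoints 2a, 2b, 3a and 3b, together with the undefined medication subgroup in SAP 3.10. The primary result on the full analysis set is unaffected. The number of subjects involved cannot be derived, so no size of bias is claimed. The conclusion assumes that the SAP's definition of the primary endpoint governs and that no case report form outside these documents already records medication changes after Visit 1. It should be corrected before the PP analyses are run, but it does not threaten the study's main conclusion.

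**What to change.** 1. **SAP 3.2.** Reconcile the bullet with Protocol 3.3 so that the PP criterion names Parkinson's medications through study exit. Drop the antidepressant condition, or keep it with a stated reason and a named data source.
2. **Data source.** Add a question on medication changes since the last contact to the existing Day 14 call and to Visit 3, and cite those records in SAP 3.2. If they can no longer be collected, correct the wording anyway and state which records will be used to judge stability and what they would miss.
3. **SAP 3.10.** Define the tremor medication subgroup in the protocol's terms. A split of levodopa against other Parkinson's medication or none could be built from Visit 1 data, but it is optional.

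The cost is a few lines of SAP text and one case report form question at two contacts that already take place. Adding the question to the protocol's schedule would also need an amendment under Protocol 10.2. No new visit is needed and the sample size does not change.
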